17.6.1 Incomplete Start Date

The following rules will be applied to impute the missing numerical fields. If the stop date is complete and the imputed start date is after the stop date, then the start date will be imputed using the stop date.

- Missing day, month and year
 - The start date will be set to null.
- Missing day and month
 - 01 January will be assigned to the missing fields.
- Missing day only
 - The first day of the month will be assigned to the missing day.

17.6.2 Incomplete Stop Date

The following rules will be applied to impute the missing numerical fields. If the imputed stop date is before the start date (imputed or non-imputed start date), then the imputed stop date will be equal to the start date.

- Missing day, month and year
 - The day, month and year of the last date on study will be assigned to the missing fields.

- Missing day and month
 - If the year of the incomplete stop date is the same as the year of the last date on study, then the day and month of the last date on study will be assigned to the missing fields.
 - If the year of the incomplete stop date is not the same as the year of the last date on study, then 31 December will be assigned to the missing fields.
- Missing day only
 - If the month and year of the incomplete stop date are the same as the month and year of the last date on study, then the day of the last date on study will be assigned to the missing day.
 - If the month and year of the incomplete stop date are not the same as the month and year of the last date on study, then the last day of the month will be assigned to the missing day.

17.7 Missing Date Information for Adverse Events

17.7.1 Incomplete Start Date

The following rules will be applied to impute the missing numerical fields. If the stop date is complete and the imputed start date is after the stop date, then the start date will be imputed using the stop date.

- Missing day, month and year
 - The day, month and year of the date of the first dose of investigational product will be assigned to the missing fields.
- Missing day and month
 - If the year of the incomplete start date is the same as the year of the date of the first dose of investigational product, then the day and month of the date of the first dose of investigational product will be assigned to the missing fields.
 - If the year of the incomplete start date is not the same as the year of the date of the first dose of investigational product, then 01 January will be assigned to the missing fields.
- Missing day only
 - If the month and year of the incomplete start date are the same as the month and year of the date of the first dose of investigational product, then the day of the date of the first dose of investigational product will be assigned to the missing day. If the month and year of the incomplete start date are not the same as the month and year of the date of the first dose of investigational product, then the first day of the month will be assigned to the missing day.

17.7.2 Incomplete Stop Date

No imputation is needed for AE stop dates.

17.8 Missing Severity Assessment for Adverse Events

If the severity is missing for an AE starting before the date of the first dose of the investigational product, then a severity of "Mild" will be assigned. If the severity is missing for an AE starting on or after the date of the first dose of the investigational product, then a severity of "Severe" will be assigned. The imputed values for severity assessment will be used for incidence summaries, while the actual values will be used in data listings.

17.9 Missing Relationship to Investigation Product for Adverse Events

If the relationship to investigational product is missing for an AE starting on or after the date of the dose of the investigational product, a causality of "Related" will be assigned. The imputed values for relationship to the investigational product will be used for incidence summaries, while the actual values will be presented in data listings.

17.10 Character Values of Clinical Laboratory Variables

If a character value collected from the CRF contains ">" sign, the numeric value used in the analysis will be calculated from the numeric part of the collected value times 2. For example, given a collected clinical laboratory result of "> 75", the numeric value used in the analysis will be 150.

If a character value collected from the CRF contains "<" sign, the numeric value used in the analysis will be calculated from the numeric part of the collected value divided by 2. For example, given a collected clinical laboratory result of "< 120", the numeric value used in the analysis will be 60.

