2.5 Determination of Sample Size

The enrollment goal for this study is to randomize at least 66 subjects to ensure 54 subjects complete both treatment periods (44 for the crossover sequences, 10 for the active/active sequence).

For the primary efficacy endpoint, the normalized number of angioedema attacks (NNA), a sample of 44 subjects will provide 90% power at an alpha level of 0.025 (1-sided) to detect a difference of 1.0 attacks per month between active treatment and placebo assuming a standard deviation of the difference of 2.0.

Regarding the analysis of the key secondary endpoint, the proportion meeting criterion P_R relative to placebo, 44 subjects will provide 90% power to test the hypothesis H_0 : proportion

Page 18

 \leq 0.2 against H₁: proportion >0.2, assuming the true proportion is 0.44 by using a 1-group Chi-square test at an alpha level of 0.025 (1-sided).

With respect to safety, a Safety Analysis Set of 60 subjects ensures that if the true population event proportion of any subject with a particular event is at least 5%, then the probability of observing at least 1 such event in the Safety Analysis Set is >95%.

The sample size calculation was conducted using nQuery + nTerim 2.0.

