11.2 Clinical Laboratory Variables

Descriptive statistics for clinical laboratory values (in SI units) and changes from baseline at each assessment time point (baseline, 8a, 16a, 24a, 28a, 8b, 16b, 24b and 28b) will be presented by treatment for the following clinical laboratory variables:

Hematology: WBC count (total and differential), RBC count, hemoglobin, hematocrit, and platelet count.

Biochemistry: aspartate aminotransferase (AST), alanine aminotransferase (ALT), alkaline phosphatase (ALP), creatine phosphokinase (CPK), Blood urea nitrogen (BUN), creatinine, carbon dioxide (CO2), albumin, total protein, glucose, potassium, sodium, chloride, and phosphorus

Coagulation: Prothrombin time (PT), international normalized ratio (INR), activated partial thromboplastin time (aPTT) and D-dimer.

Urinalysis with microscopy: pH, Dipstick (protein, glucose, ketones, hemoglobin), Specific gravity, Microscopic evaluation (red blood cells, white blood cells, crystals, casts, bacteria).

Clinical laboratory test values are potentially clinical important (PCI) if they meet either the low or high PCI criteria listed in Table 6 and fall outside the laboratory's normal range in the same direction (high or low) as their PCI criteria. Subjects with post-dose PCI values will be summarized by treatment and also listed. In addition, The number of subjects with a nonmissing result, and the number and percentage of subjects with a clinically significant result less than the lower limit of normal, non-clinically significant result less than the lower limit of normal, within the normal range, non-clinically significant result more than the upper limit of normal, and clinically significant result more than the upper limit of normal will be summarized by visit and treatment.
			Criteria for Clinic Abnormalities ¹	ally Significant Laboratory
Parameter	Age Range	Gender	Low	High
Hematology	. 11		N T 4	
Eosinophils (%)	All	Male, Female	NA	>4 x ULN
Hematocrit	All	Male, Female	<0.6 x LLN	>1.3 x ULN
Hemoglobin	All	Male, Female	<0.6 x LLN	>1.3 x ULN
Neutrophils (%)	All	Male, Female	<0.5 x LLN	NA
Platelets	All	Male, Female	<0.4 x LLN	>2 x ULN
Leukocytes (WBC)	All	Male, Female	<0.5 x LLN	>2 x ULN
Coagulation				
Intl. Normalized Ratio (INR)	All	Male, Female	NA	>1.5 x ULN
Activated Partial Thromboplastin Time (aPTT)	All	Male, Female	NA	>2.0 x ULN
Chemistry				
Albumin	All	Male, Female	<0.6 x LLN	NA
Alkaline Phosphatase	All	Male, Female	NA	>3.0 x ULN

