17. DATA HANDLING CONVENTIONS

17.1 General Data Reporting Conventions

Continuous variables will be summarized using the following descriptive statistics: n, mean, SD, median, minimum, and maximum. Categorical and count variables will be summarized by the number of subjects (n) and the percent of subjects in each category.

Unless specified otherwise, min/max will be presented to the same decimal places as the raw data. Percentage, mean and median will be presented to 1 more decimal places than the raw data. Standard deviation and standard error will be presented to 2 more decimal places than the raw data.

In addition, *p*-values will generally be presented to 4 decimal places; values less than 0.0001 will be presented as <0.0001.

Treatment Columns Displayed in Summary Tables

The treatment columns displayed will differ between summary tables. Tables that summarize information only from the prior treatment or post-treatment periods will generally have the following treatment columns displayed:

Sequence A/B

Sequence B/A

Sequence A/A

Total

Tables that summarize efficacy and safety information only from the treatment period will generally have the following treatment columns displayed:

Treatment A: 2000 IU C1 INH

Treatment B: Placebo

Total (if needed)

Tables that summarize efficacy and safety information from the treatment period and treatment sequence will generally have the following treatment columns displayed:

Sequence A/B: Period 1: 2000 IU C1 INH

Sequence A/B: Period 2: Placebo

Sequence B/A: Period 1: Placebo

Sequence B/A: Period 2: 2000 IU C1 INH

Sequence A/A: Period 1: 2000 IU C1 INH

Sequence A/A: Period 2: 2000 IU C1 INH

Tables that summarize efficacy and safety information from the treatment period with different treatment sequence combinations will generally have the following treatment columns displayed:

Treatment A from Sequence A/B and B/A: 2000 IU C1 INH

Treatment A from Sequence A/A: 2000 IU C1 INH

Treatment A Overall: 2000 IU C1 INH

Treatment B: Placebo

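### The blanket rule in SAP 17.10 that doubles '>' and halves '<' laboratory results would put impossible values into the urine pH and specific gravity summaries if such results occur

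*SAP*

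**What the plan says.** SAP 17.10 sets one substitution rule for laboratory results that arrive as text. For a result with a '>' sign, the analysis value "will be calculated from the numeric part of the collected value times 2"; the worked example turns '> 75' into 150. For a result with a '<' sign, it "will be calculated from the numeric part of the collected value divided by 2"; the worked example turns '< 120' into 60. The section names no analyte to which the rule does not apply and sets no plausibility limit.

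SAP 11.2 plans "Descriptive statistics for clinical laboratory values (in SI units) and changes from baseline at each assessment time point", by treatment. Its list of variables includes "Urinalysis with microscopy: pH, Dipstick (protein, glucose, ketones, hemoglobin), Specific gravity, Microscopic evaluation". SAP 17.1 fixes the statistics: "Continuous variables will be summarized using the following descriptive statistics: n, mean, SD, median, minimum, and maximum".

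On listings, SAP 17.8 and 17.9 (missing adverse event severity and relationship) each say that the actual value is shown. SAP 17.10 has no such sentence.

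**The concern.** A '>x' result says only that the true value lies above x. Replacing it by 2x, or '<x' by x/2, is a rough convention that can be tolerated for a concentration measured from zero. It fails for two variables in the SAP's own list. Specific gravity is a ratio to water that varies in the second and third decimal place around a value just above 1. pH is a logarithmic scale. Doubling or halving either one gives a number that no urine sample could have.

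A programmer who follows the SAP exactly would put such numbers into the mean, SD, minimum or maximum, and change from baseline in the safety tables. Because the specific gravity range is so narrow, one substituted value is enough to swamp the spread of all the others. A programmer who notices must depart from the SAP after it was finalised.

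**Working it through.** **The SAP's own examples.** 75 × 2 = 150 and 120 / 2 = 60. Both reproduce, so the rule is read as intended.

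**Applied to specific gravity and pH.** The documents give no reporting limits, so the limits here are assumptions.
- '>1.030': 2 × 1.030 = 2.06. Over assumed limits of 1.025 to 1.060 the result is 2.05 to 2.12. Any limit above 1.000 gives more than 2.
- '<1.005': 1.005 / 2 = 0.5025.
- pH: any '>' limit above 7 gives more than 14; an assumed '>9' becomes 18.

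**Effect on mean and SD.** Inputs: n = 60, the Safety Analysis Set size in SAP 2.5; k results reported as '>1.030'; the other n − k results with mean m = 1.018 and SD s = 0.007 (both assumed). With v the value analysed for the '>' results and d = v − m:

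mean = m + k·d/n

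SD² = [(n − k − 1)·s² + (k(n − k)/n)·d²] / (n − 1)

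Under the SAP rule v = 2.06 and d = 1.042. For k = 1:
- mean = 1.018 + 1.042/60 = 1.0354
- SD² = [58 × 0.000049 + (59/60) × 1.0858] / 59 = 0.01814, so SD = 0.135

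| '>1.030' results in 60 | Limit analysed (1.030): mean (SD) | SAP rule (2.06): mean (SD) |
|---|---|---|
| 0 | 1.0180 (0.0070) | 1.0180 (0.0070) |
| 1 | 1.0182 (0.0071) | 1.0354 (0.1347) |
| 3 | 1.0186 (0.0073) | 1.0701 (0.2291) |
| 6 | 1.0192 (0.0076) | 1.1222 (0.3153) |

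One result multiplies the SD by about 19 (0.1347 / 0.0071). Using s = 0.006 leaves 0.135 unchanged to three decimals, because the d² term dominates.

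**Table cells.** The summaries are by treatment at each time point, so cells are smaller than 60. With the planned allocation of 26, 26 and 14, a period has 26 subjects on placebo and 26 + 14 = 40 on active. The same formulas with k = 1 give mean 1.058 and SD 0.204 for n = 26, and mean 1.044 and SD 0.165 for n = 40. The figures for 60 therefore understate the effect on a single cell.

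**Change from baseline.** A subject going from 1.020 to '>1.030' is recorded as 2.06 − 1.020 = +1.040. With the limit the change is 1.030 − 1.020 = +0.010.

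**PCI flags.** SAP Table 6 has no criterion for pH, specific gravity or D-dimer, so these variables cannot be flagged. For analytes that do have a high criterion, doubling alone carries a result over the cut-off only if the reporting limit lies between half and all of it; for ALT (cut-off 3.0 × ULN) that is 1.5 to 3.0 × ULN. The documents identify no such analyte.

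**The case against.** The strongest reply is that the harm is hypothetical and peripheral. It needs '>' or '<' results on these variables, and neither document says that any are expected. Protocol 9.9 names hematology, chemistry and coagulation for its laboratory summaries; only the SAP adds urinalysis. Of the time points in SAP 11.2, urinalysis is scheduled at baseline, 28a and 28b only. The median is also reported and hardly moves. SAP 17.3 puts all assessments in the data listings. All of this stands and limits the size of the point, but it does not make the rule right for pH or specific gravity.

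A second reply concerns scope. A reader might infer that doubling should be dropped for every analyte because it invents a value. The documents do not support going that far. Any single substituted value is invented, including the limit itself, which always understates a '>x' result and can hide a value above a PCI cut-off. Doubling errs towards flagging, in line with the cautious defaults in SAP 17.8 and 17.9, where a missing on-treatment severity becomes severe and a missing relationship becomes related. That choice is defensible for concentration assays.

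A reader might also infer that the rule creates false PCI flags. That is not shown. The true value behind a '>x' result may well exceed the cut-off, so a flag that depends on doubling is unsupported by the reported result, not proven wrong.

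**Conclusion.** The point holds for urine pH and specific gravity: the rule is wrong as written for them, and minor. That doubled values on these scales are impossible does not depend on the exact limit, since it follows for any specific gravity limit above 1.000 and any pH limit above 7. The size does rest on assumptions: a limit of 1.030, and a mean of 1.018 with SD 0.006 to 0.007 for the remaining results. On those, one '>' result in 60 takes the SD to about 0.135 and shifts the mean by about 0.017.

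It would be too strong to say that the safety tables will be corrupted. With no censored results on these two variables nothing changes, and the documents do not say how many to expect. The primary and key secondary endpoints rest on attack counts and are not affected.

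**What to change.** Add to SAP 17.10 that for urine pH and specific gravity the reporting limit itself is used as the analysis value for both '>' and '<' results, and that listings show the result as collected, as SAP 17.8 and 17.9 already provide for adverse event data.

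For the other analytes the existing rule can stay. At most, state that a PCI flag that arises only because a result was doubled is marked as such in the listing.

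The cost is a sentence or two in the SAP and a small change to the laboratory derivation. No new data, design change or sample size is involved.

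Nothing is lost by exempting the two variables. The limit still understates a '>' result and overstates a '<' result, but it gives a possible value, and Table 6 has no criterion for either variable, so no flag can be missed.

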17.11 Handling Missing HAE Attack Data

If there are incomplete attack start/end dates in the collected data, the following imputations will be performed in a sequential order of the incomplete dates within each subject. This is to ensure that multiple identical incomplete dates will be imputed as separate attacks.

- Imputation of start date for an attack:
- If the attack start day is unknown and there is no previous attack in the same month, the first day of the month will be assigned to the missing field.
- If the attack start day is unknown and there is at least one previous attack in the same month, the previous attack end date + 1 will be assigned to the missing field.
- Imputation of end date for an attack:

The imputation of end date for an attack will follow one of the following 3 rules, whichever is the earliest:

- The start date of the current attack + 6 if attack end date is partially or completely missing.
- The start date of the next attack -2 if attack end date is partially or completely missing.
- The last day of the month if attack end date is partially missing with missing day only.

Page 54

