3.1 Study Design and Flow Chart

This is a randomized, double-blind, placebo-controlled, two-period, three-sequence, partial crossover study (Figure 7). The design was chosen to optimally address the joint protocol objectives of establishing efficacy (relative to placebo) and safety (ie, enrolling an adequate number of subjects to have precision of estimation to detect or rule out safety signals).

Additionally, this design maximizes the number of subjects exposed to C1 esterase inhibitor [human] liquid for injection and minimizes subject exposure to placebo, while having adequate subject exposure to placebo to assess efficacy.

Subjects will be screened within 21 days prior to randomization. Subjects are required to have a history (based on subject recall and medical records) of ≥ 2 attacks per month on average per inclusion criterion #3. At least 66 eligible subjects will be randomized to 1 of 3 treatment sequences prior to the first dose of investigational product in Treatment Period 1 (ie, Dosing Day 1a) using interactive response technology (IRT). Randomization of subjects will be stratified by use of prophylactic therapy with C1 INH at the time enrollment.

Figure 7 Study Design Flow Chart

Each treatment period will be 14 weeks, without a washout between the 2 periods. The omission of a washout period is to minimize the duration that subjects will be without active treatment. It is recommended that the twice weekly dosing schedule (every 3 or 4 days) be maintained between the last dose of investigational product in Treatment Period 1 and the first dose of investigational product in Treatment Period 2. Every effort should be made to complete scheduled dosing and to avoid situations where investigational product is not received. In order to prevent a missed dose, a less than 3-day interval may occur, with the recommendation of allowing at least 24 hours between doses.

All study site personnel, subjects, qualified home health professionals, and the sponsor will be blinded to treatment sequence.

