7.2.2.1 Definition of an Angioedema Attack

An angioedema attack will be defined as any subject-reported indication of swelling or pain at any location following a report of no swelling or pain on the previous day (ie, there must be a full symptom-free calendar day preceding the onset of symptoms for an attack to be considered a new attack). Therefore,

- Attacks that progress from 1 site to another will be considered a single attack
- Attacks that begin to regress and then worsen before complete resolution will be considered 1 attack
- Attacks that begin, appear to resolve, and then reappear without a symptom-free calendar day reported after the appearance of resolution will also be considered 1 attack

Note: An angioedema attack does not include swelling due to trauma, arthritis, or symmetrical nonpainful swelling of the lower extremities.

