10. EFFICACY ANALYSES

10.1 Primary Efficacy Variable(s) and Analysis

The primary efficacy analysis will be conducted over the subjects in the Full Analysis Set that are randomized to Treatment Sequence 1 (A/B) or 2 (B/A) to evaluate of the efficacy of SC administration of C1 esterase inhibitor [human] liquid for injection compared to placebo.

The primary efficacy endpoint is defined as the normalized number of angioedema attacks during a treatment period. The NNA is expressed as the number of attacks per month (ie, 30.4 days) of exposure:

NNA = 30.4 x (number of attacks during treatment period)/(days of treatment period)

If a subject discontinues during the treatment period, the denominator of the NNA will be the days on treatment for that subject; this is equivalent to the last observation carried forward imputation method to impute the missing information following the subject's discontinuation.

To test the hypothesis that the NNA of C1 esterase inhibitor [human] liquid for injection is greater than or equal to the NNA of placebo, and the alternative hypothesis that the NNA of C1 esterase inhibitor [human] liquid for injection is less than the NNA of placebo as below:

H_{0:} μ _{C1 INH} - μ placebo ≥ 0 VS H_{1:} μ _{C1 INH} - μ placebo < 0

A linear mixed effect model will be performed to analyze the primary efficacy endpoint with period, sequence, use of prophylactic therapy with C1 INH, which is derived by long-term prevention with C1 INH at randomization, and treatment as fixed effects, and subject nested within sequence as a random effect. If the variance-covariance matrix of random effects is not positive definite, a mixed effect model with the same fixed effects and subject nested within sequence as repeated measurements will be performed instead; the repeated measurement is equivalent to the random effect in terms of statistical testing and point estimates of coefficients of fixed effects, however, the variance covariance matrix of random effects will not be estimated. The mean treatment difference ($\mu_{C1 \text{ INH}} - \mu_{placebo}$) will be estimated with a 95% CI provided. The upper confidence bound of 95% CI must be less than 0 in order for C1 INH to be considered superior to the placebo.

A summary of NNA during each treatment period by treatment sequences will be provided for the Full Analysis Set.

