10.2 Key Secondary Efficacy Variable(s) and Analysis

The key secondary efficacy variables are listed as following:

- 1. The proportion of subjects meeting the criterion of at least a 50%, 70%, 90% and 100% reduction in the NNA during the 2000 IU C1 esterase inhibitor [human] liquid for injection treatment period relative to the placebo period.
- 2. The NNA excluding the first 2 weeks of each treatment period.
- 3. The proportion of subjects meeting the criterion of at least a 50%, 70%, 90% and 100% reduction in the NNA for the 2000 IU C1 esterase inhibitor [human] liquid for injection treatment period relative to the placebo period excluding the first 2 weeks of each treatment period.

Key secondary efficacy endpoints 1 and 3 are defined as achieving a \geq 50% reduction in the NNA (P_R) during the 2000 IU C1 esterase inhibitor [human] liquid for injection treatment period relative to the placebo period.

The Key secondary endpoints 1 and 3 will be analyzed as the proportion of subjects meeting the above clinical response criterion (P_R). The analysis will be conducted over the Full Analysis Set from the first two treatment sequences. The null hypothesis is that P_R is less than or equal to 0.2, and the alternative hypothesis is that P_R is greater than 0.2 as below:

$$H_{0:} P_{R} \leq 0.2$$
vs
$$H_{1:} P_{R} > 0.2$$

The proportion P_R will be estimated with an exact 95% CI. The lower limit of the 95% CI for the proportion will be compared with 0.2. This is equivalent to testing the null hypothesis against the alternative hypothesis at a 1-sided alpha level of 0.05 using the binomial distribution.

Analysis of key secondary endpoint 2 will follow the same methods (ie, the linear mixed effect model) used for the primary efficacy endpoint.

The key secondary analyses will be performed using the Full Analysis Set and the Per-protocol Set.

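### SAP 17.11 imputes unknown attack start days with no limit at first dose or period start, so an on-treatment attack can be dated before dose 1 or counted under the other treatment

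*SAP*

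**What the plan says.** SAP 17.11 has two rules for an attack whose start day is unknown. The first covers "no previous attack in the same month, the first day of the month will be assigned to the missing field". The second covers "at least one previous attack in the same month, the previous attack end date + 1 will be assigned to the missing field". A missing end date takes the earliest of three candidates, one of which is "The start date of the next attack -2 if attack end date is partially or completely missing". The section gives the purpose of working through the dates in order: "This is to ensure that multiple identical incomplete dates will be imputed as separate attacks". It states no lower limit at first dose or at the start of a treatment period, and no upper limit at a known end date. No other section of the text available for review adds one.

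Four other places make the date matter:

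- SAP 10.1 defines the primary endpoint per period: "NNA = 30.4 x (number of attacks during treatment period)/(days of treatment period" (closing bracket not shown).
- Protocol 3.1: "Each treatment period will be 14 weeks, without a washout between the 2 periods".
- SAP 10.2, key secondary 2: "The NNA excluding the first 2 weeks of each treatment period". Key secondary 3 applies the same exclusion to the responder criterion.
- Protocol 7.2.2.1 on what makes a new attack: "there must be a full symptom-free calendar day preceding the onset of symptoms for an attack to be considered a new attack".

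SAP 17.7.1 handles adverse events differently. An event with an unknown day, in the same month and year as first dose, is dated to the first-dose day. An imputed start that falls after a known stop date is pulled back to it.

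**The concern.** The imputed date moves an attack backward in time, and nothing stops it at a boundary that decides how the attack is counted. There are three such boundaries: dose 1, the crossover, and the end of each excluded 2-week window. In sequences A/B and B/A, an attack moved from Period 2 into Period 1 changes treatment. The error can go either way. In A/B a placebo attack is counted as active; in B/A an active attack is counted as placebo. The rule can do this even when the diary or CRF already shows the period in which the attack began, so the imputation would override information the trial holds.

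**Working it through.** **Plan's own example.** SAP 19.1 has symptoms on days 1–2, 4–6 and 8–11. Grouping with at least one symptom-free day between attacks gives 3 attacks. The maxima are 2 + 3 + 3 = 8 and the daily scores 4 + 6 + 9 = 19. Both match the SAP.

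**Dates.** Take a hypothetical dose 1 on 20 Sep 2016. Period 2 starts 98 days later, on 27 Dec 2016, and 1 Dec is Day 73 of Period 1.

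| True onset | Recorded as | Earlier attack that month | Imputed start | Counted in |
|---|---|---|---|---|
| 29 Dec (Period 2) | Dec 2016 | none | 1 Dec | Period 1 |
| 29 Dec (Period 2) | Dec 2016 | ended 10 Dec | 11 Dec | Period 1 |
| 25 Sep (Period 1) | Sep 2016 | none | 1 Sep | 19 days before dose 1 |

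Such dates are not unusual. The first of the month precedes dose 1 for 354 of the 366 possible first-dose dates in a leap year.

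**Size per attack.**

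- One attack over 98 days: 30.4/98 = 0.31 NNA.
- One attack in key secondaries 2 and 3 (84 days): 30.4/84 = 0.36.
- One attack moved across the crossover: 2 × 0.310 = 0.62 in that subject's difference.
- The same in a mean over 44 subjects (SAP 2.5): 0.620/44 = 0.014.

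**Share at risk.** Only attacks in the calendar month that contains the start of the period can move. For a month of L days, the days left, summed over first-dose dates from the 2nd on, are L(L − 1)/2. Over a leap year this totals 5401, and 5401/366/98 = 0.15. The range is 0 to 30/98 = 0.31. This is an upper bound, because an earlier attack within the same period pulls the imputed date back into that period.

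**Total effect, on assumed inputs.** The documents give neither a missing-date rate nor attack rates by arm. Assume 3 attacks per month on placebo, 2 on active, and 22 subjects per crossover sequence.

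- A/B Period 2 attacks: 22 × 3 × 98/30.4 = 212.8.
- B/A Period 2 attacks: 22 × 2 × 98/30.4 = 141.8.
- At 1% missing, at most (212.8 + 141.8) × 0.15 × 0.01 = 0.53 attacks move.
- The two directions partly cancel: (212.8 − 141.8) × 0.0015 × 0.0141 = 0.0015.

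| Missing start days (assumed) | Attacks moved, at most | Net shift toward no difference |
|---|---|---|
| 1% | 0.5 | 0.0015 |
| 5% | 2.7 | 0.0075 |
| 10% | 5.3 | 0.015 |

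The planned difference is 1.0. Assumed rates of 4/3 and 2.5/1.5 give the same net shift. A simulation with random calendar starts and 2-day attacks showed 5–9% of Period 2 attacks with a missing start day moving, rather than 15%.

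**Responder criterion.** In A/B, 8 placebo against 4 active attacks is a 50% reduction and a response. Move one and it is 7 against 5, or 1 − 5/7 = 29%, no response. In B/A, a true 7 against 5 becomes 8 against 4, a false response.

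**What a plain floor would do.** Take dose 1 on 5 Sep 2016, so Period 2 starts on 12 Dec. An attack on 29 Dec is Day 18 and countable in key secondaries 2 and 3. Recorded only as December, with no earlier attack that month, a floor at the start of the period dates it 12 Dec. That is Day 1, inside the excluded window.

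**The case against.** The strongest reply is that the trigger is remote and the effect negligible. Subjects complete an electronic diary daily, onset date and time are both collected (Protocol 7.2.2.2), the AAS is recorded daily, and data are checked against source. A month known with the day missing should be rare. This stands, and it is why the point carries no claim about the trial's conclusion.

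A second reply is that no text says an imputed day overrides a known period, and detailed table specifications are in a separate document. That is fair. But no text says the recorded period governs either, and the listed attack fields include no period or visit link. The SAP should settle it.

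A third reply concerns the remedy. A floor at the start of the period alone would turn a roughly balanced error around the 2-week window into a one-directional loss of attacks. Using the end date to fix the period would also misplace an attack that straddles the crossover: with Period 2 from 27 Dec, onset 26 Dec and end 29 Dec would be forced into Period 2. Both objections are right, and the fix below allows for them.

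A reader might infer that the previous-end + 1 rule loses attacks by merging neighbours. In the SAP 19.1 example, an unknown start for attack 2 would become day 3, and regrouping would give 2 attacks instead of 3. The documents do not support that reading. Protocol 7.2.2.2 calls for a separate CRF per attack, SAP 19.4 item 21 makes its absence a major deviation, and SAP 17.11 aims to keep attacks separate. When CRF records are counted, the count is unchanged.

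**Conclusion.** The point holds in limited form. As written, SAP 17.11 can date an on-treatment attack before dose 1 or under the other treatment, even when its period is known. The text and the date arithmetic establish that this can happen. How often is unknown, because no missing-date rate is given.

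A reader might infer that this threatens the primary result or favours active treatment. It does not. Even at an assumed 10% missing, with every attack at risk moved, the net shift is about 0.015 against a planned 1.0. If placebo attacks are the more frequent, it is toward no difference. The practical exposure is an individual subject's 50% responder status and the 2-week exclusion. The rule should be corrected because it can contradict data in hand for the primary endpoint and the correction is small.

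The + 1 spacing is a minor inconsistency with the attack definition and with the − 2 rule in the same section, and nothing more.

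**What to change.** Amend SAP 17.11 before unblinding:

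1. In both start-date rules, set the imputed start no earlier than the first-dose date of the treatment period in which onset was recorded, and no later than a known end date or the end of the known month. Where the diary or CRF does not show the period of onset and the attack could straddle the crossover, settle the period by blinded review, not by the end date alone.
2. For key secondaries 2 and 3, do not let that floor decide exclusion. Where the possible onset dates span the end of the first 2 weeks, count the attack and repeat the analysis with it excluded.
3. State that each attack CRF record counts as one attack and is not merged or dropped because of an imputed date.
4. For consistency only, change + 1 to + 2, with the limits in item 1 taking precedence where they conflict (for example, when the previous attack ended on one of the last two days of the month).

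The cost is a few lines in the SAP and in the attack-derivation code, a blinded look at any affected records, and one repeat run for each of key secondaries 2 and 3. No new data are needed.
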